8.3 SAMPLE SIZE DETERMINATION AND RATIONALE

Sample size determination is not applicable as only those subjects who are currently enrolled in PRO 140_CD 01 Treatment Substitution Study are allowed to participate in this extension study.

8.4 RANDOMIZATION AND BLINDING

This study is an open label study with one treatment arm with no randomization and blinding requirements.

8.5 INTERIM ANALYSIS

There is no planned interim analysis (IA) for efficacy. IA for safety will be conducted after all enrolled subjects complete extended treatment with PRO 140 or until study treatment is discontinued, whichever comes first.

8.5.1 Analysis Population

Subjects who have been treated and completed the treatment extension phase (or until treatment is discontinued) will be included in the analysis. All available data from these subjects will be included in the analysis.

8.5.2 Procedures

- a. Cut-off dates for review of eCRFs, data cleaning, database lock and analysis will be established based on an estimated target date of all enrolled subjects completing pre-defined treatment period.
- b. All data received by the cutoff date will be entered, validated, queries generated and resolved or pending queries documented.
- c. The database will be locked for IA.
- d. The statistician will generate planned data and information for the DMC, as described below.

8.5.3 Data and Information Provided to DMC

The DMC will receive: AEs, SAEs, labs, ECGs, vital signs, and all other safety related variables identified per the DMC Charter. No inferential statistics will be conducted for this interim analysis.

8.5.4 Type I Error Rate Adjustment

No type I error adjustment will be made due to this safety analysis for this proof of concept study.

8.6 GENERAL STATISTICAL CONSIDERATIONS

8.6.1 Analysis Populations

8.6.1.1 Intent-to-Treat Population

The Intent-to-Treat (ITT) population is defined as the set of subjects who have at least one dose of PRO 140 and have at least one post-treatment efficacy assessment for viral load.

8.6.1.2 Per Protocol Population

The Per Protocol (PP) population is defined as the set of subjects who meet the ITT population requirements, and were not associated with a major protocol violation. This population will be identified before the database lock. The PP population will be the primary analysis population for the analysis of primary and secondary endpoints.

8.6.1.3 Safety Population

The Safety population is defined as all subjects who received at least one dose of PRO 140. This population will be used for the analysis of safety parameters.

8.6.2 Statistical Methods

All collected study data will be presented in subject data listings. Statistical analyses will be performed using SAS® for Windows, version 9.3 or later.

A SAP will be developed and approved before the database is locked. The SAP will present the detailed statistical methodology to be used in analyzing the efficacy and safety data from this trial.

8.6.3 Prognostic Factors/Covariates

There are no pre-planned covariates analyses of the data from this proof of concept study.

8.6.4 Handling of Missing Data

For the per protocol analysis of efficacy endpoints there will be no imputation of missing data. However, missing data will be imputed using different methods that will be detailed in the SAP for the ITT analysis of the primary and secondary endpoints.

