Name of Study Product: PRO 140 (Humanized monoclonal antibody to CCR5) Comparator: Historical Control	
Protocol Number: PRO 140_CD 01-Extension	Indication: Human Immunodeficiency Virus Type-1 (HIV-1) Infection

 During the Treatment Extension Phase, if virologic failure occurs or have met any other criteria for discontinuation of study treatment as specified in section 5.2 of the PRO 140_Treatment Substitution Extension Study protocol. 
Subjects who experience virologic failure (defined as two consecutive HIV-1 RNA levels of ≥ 400 copies/ml separated by at least 3 days) at any time during the Treatment Extension Phase will undergo the Virologic Failure (VF) Visit assessments and then exit the Treatment Extension Phase to enter the Follow-up Phase of the study.
 
Subjects who do not experience virologic failure will enter the Follow-up Phase of the study at the end of Treatment Extension Phase.
	

Follow-up Phase:
 
Duration of Follow-up Phase is determined based on whether or not subject has experienced virologic failure during the Treatment Extension Phase.
 
 Subjects who experience virologic failure will be followed up every 4 weeks until the viral suppression is achieved (i.e., plasma HIV-1 RNA levels return to <50 copies/mL) Subjects who do not experience virologic failure at the end of Treatment Extension Phase, will be followed up every 2 weeks for total of 4 weeks. 
➤ Note: Virologic failure subjects will have a long term safety follow up visit once a year within 2 years of completing the last VF-FU visit.
	

Duration of Study:
 
 Screening Phase: 14 ± 3 days Treatment Extension Phase: Weekly \pm allowed windows (± 3 days). Follow-up Phase: 
 Virologic Failure: Until viral suppression is achieved Non-Virologic Failure (NVF): 4 weeks 
Total Study Duration:
 
Weekly until IP receives marketing approval or IND is withdrawn by Sponsor. [Does not include additional follow-up time for virologic failure subjects]
	

Inclusion Criteria: Potential subjects are required to meet all of the following criteria for enrollment into the study.
 
 Subjects who have completed 12 weeks of treatment in PRO 140_CD 01 study without experiencing virologic failure. 	

Name of Sponsor: CytoDyn Inc.	

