8.7.4 Efficacy Analysis

8.7.4.1 Primary Analysis

The primary analysis will be conducted on the PP population.

The primary efficacy endpoint for this study is time to virologic failure after initiating PRO 140 monotherapy.

Virologic failure is defined as two consecutive HIV-1 RNA levels of ≥ 400 copies/ml separated by at least 3 days.

The time to virologic failure for the subjects treated with PRO 140 monotherapy will be compared to a historical data (i.e., time to HIV-1 RNA viral load > 500 copies/mL of 29 days). The statistical comparison will be conducted using Wilcoxon rank sum test and the median time to virologic failure for this study will be compared to 30 days.

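### The primary analysis of time to virologic failure names an ordinary rank sum test and a median, with no method for subjects whose follow-up ends without failure

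*Protocol*

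**What the plan says.** Protocol 8.7.4.1 defines the endpoint: "The primary efficacy endpoint for this study is time to virologic failure after initiating PRO 140 monotherapy". It fixes the population ("The primary analysis will be conducted on the PP population") and the test ("The statistical comparison will be conducted using Wilcoxon rank sum test"), and adds that "the median time to virologic failure for this study will be compared to 30 days". The historical reference is a "time to HIV-1 RNA viral load > 500 copies/mL of 29 days". The synopsis (Efficacy Analysis) repeats this, and 8.7.4.3 carries the same methodology to the ITT population. No section gives a censoring rule for this trial. Kaplan-Meier is mentioned only for the historical data, in the caption of Figure 1-1.

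The protocol expects subjects who do not fail:

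- Section 4.2 sends subjects without failure to follow-up at the end of treatment, and separately provides for those who stop for reasons other than failure.
- Section 5.2.1 lists such reasons, including pregnancy and a wish by the subject or clinician to restart antiretroviral therapy (ART).
- Section 5.2 adds withdrawal for adverse events and by sponsor decision.

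The synopsis gives the study duration as "Weekly until IP receives marketing approval or IND is withdrawn by Sponsor", while 4.2 and footnotes to the schedule tables still refer to 161 weeks.

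On missing data, 8.6.4 says: "For the per protocol analysis of efficacy endpoints there will be no imputation of missing data". It leaves the ITT imputation methods to the SAP. Sections 8 and 8.6.2 place detailed methodology in the SAP.

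**The concern.** A subject who ends treatment without failure has a right-censored failure time: it is known only to exceed the time observed. An ordinary rank sum test takes each entered value as an exact time. It has no place for a censored value unless someone decides what number to enter, and 8.7.4.1 does not say. A median has the same difficulty unless its estimator allows for censoring, and none is named.

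Everyone enrolled has already completed 12 weeks without failure (3.3.1), and the objective is long-term efficacy (section 2). Long failure-free times are therefore what the study exists to measure. If they are dropped, the longest responders leave the estimate. If they are entered as failures at last visit, the estimate depends partly on when subjects left or when the sponsor ended treatment. The median is the figure that readers will take as the duration of suppression.

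**Working it through.** The protocol states no sample size calculation, failure rate, drop-out rate or power, so there is no figure of its own to reproduce. The check is a simulation on stated assumptions.

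**Inputs from the protocol.** N up to 28 (synopsis); 23 subjects finished the parent study without failure (1.5.2.7); 161 weeks as a treatment length (4.2); reference value 30 days (8.7.4.1).

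**Assumed inputs.** Exponential failure times; true median 100 or 160 weeks; censoring spread uniformly over weeks 60-161, with drop-out of 20% per 161 weeks; alternatively a common cutoff at week 161 without drop-out.

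**Share failing by week 161** for true median m is 1 - 2^(-161/m). For m = 100 this is 1 - 2^(-1.61) = 0.67. For m = 160 it is 0.50.

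**Results, n=23, weeks:**

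| Follow-up | True median | Failures only | Non-failures entered as failures | Kaplan-Meier |
|---|---|---|---|---|
| Staggered, 20% drop-out | 100 | about 43 | about 70 | about 93 when reached (about 81% of runs) |
| Staggered, 20% drop-out | 160 | about 47 | about 81 | reached in about 41% of runs |
| Common cutoff, no drop-out | 100 | about 60 | about 102 | not tabulated |

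The Kaplan-Meier figure of 93 averages only the runs in which the median is reached, which pulls it somewhat below 100.

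**Closed-form check of the failures-only value under a common cutoff.** With hazard ln 2 / 100 = 0.00693 per week, the median among those failing by week 161 solves F(t) = 0.672/2 = 0.336. So t = -ln(0.664)/0.00693 = about 59 weeks, in line with the simulated 60.

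**A second set of assumptions** (n=28, censoring uniform over weeks 26-161, no other drop-out, results in days):

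- 75% failing by week 161, true median 564: failures-only about 259, entered as failures about 381, Kaplan-Meier about 562.
- 50% failing, true median 1127: about 305 and 495, with the Kaplan-Meier median not reached in about 60% of runs.
- Common cutoff, 75% failing: the all-subjects median is about 581 against 564.
- Common cutoff, only 25% failing: the all-subjects median sits at the cutoff (about 1127) against a true 2715, and the Kaplan-Meier median is not reached.

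So the all-subjects median is nearly right under a common cutoff only when more than half fail before it.

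**The 30-day comparison.** In the first set of assumptions the lowest naive median is about 43 weeks, or 43 x 7 = 301 days, about ten times the reference. A subject followed failure-free past day 30 is known to exceed 30 days whatever happens later. If all subjects do so, a two-sided sign test gives 2 x 0.5^23 = 2.4e-7 (n=23) or 2 x 0.5^28 = 7.5e-9 (n=28). Censoring after day 30 does not enter that calculation.

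**The case against.** The strongest reply is that detailed methods belong to the SAP, which is not shown, and that a Kaplan-Meier median fits the wording of 8.7.4.1. The second half stands: the protocol names no estimator, so it cannot be said to prescribe a plain sample median. The first half stands only in part. The test is not deferred; it is named in the protocol, repeated in the synopsis and extended to ITT. A SAP that used a censored-data method would depart from the named test, not elaborate it.

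Four stronger readings are tempting and are not supported.

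- A reader might infer that the no-imputation rule in 8.6.4 removes non-failures. It concerns missing data, and censored-data methods need no imputation.
- A reader might infer that non-failures will be dropped or counted as failures. No section prescribes either; they are the two likely mishandlings when no rule is given.
- A reader might infer that a rank-based analysis can never use such subjects. With a common cutoff after the last failure they can share the top rank.
- A reader might fear a false finding of efficacy from the bias. In the staggered scenarios the bias runs downward, against the drug, and the stated 30-day comparison barely changes.

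It is also fair to say that the failure, censoring and drop-out patterns are all assumed, in a study that calls itself proof of concept.

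**Conclusion.** The concern holds in a limited form. Section 8.7.4.1 fixes an ordinary rank sum test and a median for an endpoint that will be right-censored, and states no way to handle the censoring, while other sections make unequal failure-free follow-up likely. Under the assumed staggered follow-up, a true median of 100 weeks would be reported as about 43 or about 70 weeks, a shortfall of 57% or 30%, depending on which mishandling was chosen. With a common week-161 cutoff, no drop-out and more than half failing, the all-subjects median is nearly right (about 102) and only the failures-only version (about 60) is badly off.

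The defect affects the reported duration of suppression, not the conclusion against 30 days. Its size rests on exponential failure and on the assumed censoring and drop-out. The protocol supplies none of these, so the figures show scale and are not predictions for this trial.

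**What to change.** In 8.7.4.1 and the synopsis, replace the rank sum test with a Kaplan-Meier analysis of time to virologic failure, and let 8.7.4.3 follow. Specify:

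- **Censoring rule:** each non-failing subject is censored at the last HIV-1 RNA sample taken on monotherapy.
- **Estimates:** the median with a Brookmeyer-Crowley 95% confidence interval, given as not reached where that applies, and failure-free probability with 95% confidence interval at fixed weeks.
- **Comparison with the historical value:** made from the lower confidence limit of that median, or by a one-sample test for censored data, so that removing the rank sum test does not leave the comparison undefined.
- **Sensitivity analysis:** restart of ART without confirmed failure counted as failure. A restart at the subject's or clinician's wish (5.2.1) may follow a rising viral load, so that censoring may be informative.

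In 8.6.4 add only a clarification that absence of failure is censoring and not missing data.

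The cost is a few sentences in the protocol and SAP and standard software output. No visit, sample or clinical rule changes. The downside is that the median may have to be reported as not reached; the fixed-week probabilities then carry the result.

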8.6.5 Multiplicity

This is a proof of concept study and there is no need for adjustment of Type I error rate.

8.7 DATA SUMMARY

8.7.1 Subject Disposition

The disposition of all subjects who sign an ICF will be provided. The number of subjects screened, received treatment, completed, and discontinued during the study, as well as the reasons for all post treatment discontinuations will be summarized. Disposition and reason for study discontinuation will also be provided as a by-subject listing.

8.7.2 Demographic and Baseline Characteristics

Demographics and baseline characteristics (i.e., Age, Gender, Time since HIV diagnosis, Viral load at Screening Visit, etc.) will be summarized using appropriate descriptive statistics.

Medical history of the subjects will also be provided as a by-subject listing.

8.7.3 Prior and Concomitant Medications

Prior and concomitant medications will be summarized for the Safety population. All prior and concomitant medications recorded in the eCRFs will be coded to generic term and all matching Anatomic Therapeutic Classification (ATC) codes using WHO Drug Summaries will be prepared using the coded terms. All prior and concomitant medications recorded in the eCRFs will also be listed.

8.7.4 Efficacy Analysis

8.7.4.1 Primary Analysis

The primary analysis will be conducted on the PP population.

The primary efficacy endpoint for this study is time to virologic failure after initiating PRO 140 monotherapy.

Virologic failure is defined as two consecutive HIV-1 RNA levels of ≥ 400 copies/ml separated by at least 3 days.

The time to virologic failure for the subjects treated with PRO 140 monotherapy will be compared to a historical data (i.e., time to HIV-1 RNA viral load > 500 copies/mL of 29 days). The statistical comparison will be conducted using Wilcoxon rank sum test and the median time to virologic failure for this study will be compared to 30 days.

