
Efficacy Analysis
 
The primary analysis of primary and secondary endpoint will be conducted on the PP population and ITT population will be used for supportive analysis.
 
The primary efficacy endpoint for this study is time to virologic failure after initiating PRO 140 monotherapy. Virologic failure is defined as two consecutive HIV-1 RNA levels of ≥ 400 copies/ml separated by at least 3 days.
 
The time to virologic failure for the subjects treated with PRO 140 monotherapy will be compared to a historical data (i.e., time to HIV-1 RNA viral load > 500 copies/mL of 29 days). The statistical comparison will be conducted using Wilcoxon rank sum test and the median time to virologic failure for this study will be compared to 30 days.
 
All the data from the secondary endpoint will also be summarized according to the variable type.
	

TABLE OF CONTENTS

STUDY TITLE.....	1
PROTOCOL SYNOPSIS	5
TABLE OF CONTENTS	11
List of Tables.....	17
List of Figures	18
List of Abbreviations.....	19
1 INTRODUCTION.....	22
1.1 Statement of Intent	22
1.2 The Problem Statement	22
1.3 Background and Historical Data	23
1.4 Name and Description of the Investigational Product.....	26
1.5 Summary of Prior Pre-Clinical And Clinical Studies	27
1.5.1 Pre-Clinical Studies with PRO 140	27
1.5.2 Clinical Studies with PRO 140.....	27
1.5.2.1 PRO 140 1101 Study.....	28
1.5.2.2 PRO 140 1102 Study.....	28
1.5.2.3 PRO 140 1103 Study.....	28
1.5.2.4 PRO 140 1302 Study.....	28
1.5.2.5 PRO 140 2301 Study.....	32
1.5.2.6 PRO 140 2101 Study.....	32
1.5.2.7 PRO 140_CD 01 Study	35
1.5.2.8 PRO 140_CD02 Study	36
1.5.2.9 PRO 140_CD02_Open Label.....	37
1.5.2.10 PRO 140_CD02 Extension Study	37
1.5.2.11 PRO 140_CD03 Study	38
1.5.2.12 PRO 140_CD03 Extension Study	38
1.6 Rationale for Dose Selection.....	42
1.7 Risks / Benefits Assessment.....	43
1.7.1 Risks/Discomfort to Subjects and Precautions to Minimize Risk.....	43
1.7.1.1 Risks associated with Temporary Discontinuation of current Antiretroviral Treatment Regimen	43
1.7.1.2 Allergic Reaction.....	44
1.7.1.3 Immune Response	44

1.7.1.4	Pregnancy	44
1.7.1.5	Venipuncture for blood sampling and Subcutaneous injection for Study Drug Administration.....	44
1.7.1.6	Risks to the Study Personnel and the Environment	44
1.7.1.7	Unknown Risks	45
1.7.1.8	Theoretical risk for increased severity of West Nile virus infection.....	45
1.7.2	Intended Benefit for Subjects	45
2	STUDY OBJECTIVES.....	46
3	STUDY DESIGN.....	47

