1.3 BACKGROUND AND HISTORICAL DATA

Based on published data from ACTG5197 trial entitled “A Phase II double-blind, randomized, placebo-controlled study to evaluate the antiretroviral effect of immunization with the MRY Ad5 HIV-1 GAG vaccine in HIV-1 infected individuals who interrupt antiretroviral drug therapy” the viral load will increase within 4 weeks after treatment interruption. The impact of treatment interruption on the CD4 cell count reduction is also observed after 4 weeks, actually the downward trend in CD4 cell counts can be observed by week 1, as it is depicted in [Figure 1-3](#).

This study was conducted in HIV infected men and women of 18 to 55 year old (inclusive), who have maintained viral load suppression for at least 24 months and had a CD4 cell counts of greater than 500 cells/mm³ and HIV-1 RNA < 50 copies/mL.

These changes in both viral load and CD4 counts are depicted in the following figures:

- a. Viral Load:** As it is depicted in [Figure 1-1](#) if the subjects who have their viral load below 50 copies/mL and their CD4 cell counts > 500 cells/mm³ have a treatment interruption, then after 4 weeks approximately 50% of them will have a viral load of >500 copies/mL; and almost 100% of the subjects will have a viral load of >500 copies/mL by 10 weeks.

Figure 1-1: Historical Data: Kalpan-Meier Estimates for the time to HIV-1 RNA >500 copies/mL

[figure not shown]
[figure not shown]

Figure 1-2 depicts the actual change in the median viral load and their 95% Confidence Intervals over a period of 16 weeks. After week 3 there is a clear increase in the viral load and by week 6 the viral load reaches the highest level and was maintained through week 16.

[figure not shown]
Figure 1-2: Historical Data: Median (95% C.I.) ATI \log_{10} HIV-1 RNA copies by treatment arm

b. CD4 Cell count: As it is depicted in Figure 1-3, subjects who have CD4 cell count of greater than 500 cells/mm³ and have a treatment interruption, a trend toward a decline in CD4 observed by week 1. This downward trend in CD4 cell count continued and after 4 weeks of treatment

interruption approximately 10% and by week 16 more than 30% reduction in their viral load was observed.

Figure 1-3: Historical Data: Median (95% C.I.) ATI CD4+ cell count by treatment arm

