3.3 ELIGIBILITY CRITERIA

3.3.1 Inclusion Criteria

Subjects must meet all of the following criteria to be included in the study:

[figure not shown]
1. Subjects who have completed 12 weeks of treatment in PRO 140_CD 01 study without experiencing virologic failure.
2. Both male and female patients and their partners of childbearing potential must agree to use appropriate birth control methods (birth control pills, barriers, or abstinence) throughout the study duration (excluding women who are not of childbearing potential and men who have been sterilized). Females of childbearing potential must have a negative urine pregnancy test prior to receiving the first dose of study drug.
3. Willing and able to participate in all aspects of the study, including use of SC medication, completion of subjective evaluations, attendance at scheduled clinic visits, and compliance with all protocol requirements as evidenced by providing written informed consent.

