8.2 DESCRIPTION OF STUDY ENDPOINTS

8.2.1 Primary Efficacy Endpoints

The primary efficacy endpoint for this study is time to virologic failure after initiating PRO 140 monotherapy.

Virologic failure is defined as two consecutive HIV-1 RNA levels of ≥ 400 copies/ml separated by at least 3 days.

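### The primary analysis names a two-sample rank sum test for one arm against a single historical number (29, then 30 days) for a different event, and on the endpoint's literal clock entry alone guarantees that number is beaten

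*Protocol*

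**What the plan says.** Section 8.7.4.1 and the Synopsis (Efficacy Analysis) give the same text. On the comparator, the trial's failure times "will be compared to a historical data (i.e., time to HIV-1 RNA viral load > 500 copies/mL of 29 days"). The method is named next: "The statistical comparison will be conducted using Wilcoxon rank sum test". The same sentence goes on to a second reference value, because there "the median time to virologic failure for this study will be compared to 30 days".

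Section 8.4 confirms the design: "This study is an open label study with one treatment arm". Section 8.2.1 defines the event as "two consecutive HIV-1 RNA levels of ≥ 400 copies/ml separated by at least 3 days". Wherever the protocol defines the primary endpoint (Synopsis, Sections 2, 8.2.1 and 8.7.4.1), time is counted from the start of PRO 140 monotherapy. Section 1.5.2.7 places that switch in the parent study, CD 01.

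Inclusion criterion 1 in Section 3.3.1 admits "Subjects who have completed 12 weeks of treatment in PRO 140_CD 01 study without experiencing virologic failure". Section 1.5.2.7 gives the same failure definition for CD 01.

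The historical figure comes from a treatment-interruption study described in Section 1.3, in subjects "who have maintained viral load suppression for at least 24 months" and with a CD4 count above 500. There, "then after 4 weeks approximately 50% of them will have a viral load of >500 copies/mL".

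**The concern.** This is the only inferential efficacy comparison in the protocol, and three things in it do not fit together.

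- **Test and design.** A rank sum test needs two samples of individual values. The text supplies one sample and a constant, and the constant changes from 29 to 30 days between consecutive sentences.
- **Event.** The historical figure is time to a value above 500, with no confirmation stated. The trial counts two consecutive values of at least 400, at least 3 days apart.
- **Clock.** Time from the start of monotherapy includes the 12 parent-study weeks that a subject had to pass without failure in order to enter.

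At stake is whether the primary result can say anything about the stated objective, long-term maintenance of suppression. As written the test cannot be run as named. Repaired in the obvious way, as a one-sample test, it is either decided by the entry criterion or measured against a short interval that says little about the long term.

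**Working it through.** **Inputs.** n = 23, the CD 01 subjects who completed 12 weeks without failure (Section 1.5.2.7), and n = 28, the planned maximum (Synopsis). Reference value 29 or 30 days (Section 8.7.4.1). Entry after 12 weeks = 84 days (Section 3.3.1). No alpha, sidedness, power or sample size is stated; where a threshold is needed, two-sided 0.05 is assumed.

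**The plan's own figure.** About half of the historical subjects were above 500 copies/mL after 4 weeks (4 × 7 = 28 days). That agrees with 29 days. The move from 29 to 30 is not explained, but its numerical effect is small.

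**The named test, taken literally.** With n subjects all above one comparator value, the exact rank sum p cannot fall below 1/(n+1) one-sided or 2/(n+1) two-sided.

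- n = 23: 1/24 = 0.042 one-sided, 2/24 = 0.083 two-sided.
- n = 28: 1/29 = 0.034 one-sided, 2/29 = 0.069 two-sided.
- A two-sided p of 0.05 or less needs 2/(n+1) ≤ 0.05, so n ≥ 39.

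**A one-sample test on the literal clock.** 84 days is 84/30 = 2.8 times the reference. When every subject exceeds 30 days, the sign test and the exact signed-rank test both give a two-sided p of 2 × 0.5^n.

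- n = 23: 2.4e-7.
- n = 28: 7.5e-9.
- Any n ≥ 6 gives p below 0.05.

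As a check, the drug was assumed to do nothing from TE1 onward: Weibull failure times with median 29 days, shape 2 or 3 (assumed), no censoring. An event-free run-in of 70, 77, 84 or 98 days was added (assumed range around 12 weeks). Tested against 30 days, 100% of simulated trials rejected in favour of the drug at both sample sizes. This does not depend on the shape, or on the run-in as long as it exceeds 30 days.

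**The same test with TE1 as time zero.** Under the same no-effect assumption with no run-in, rejection in favour of the drug falls to about 0.5% to 2% (signed-rank, two-sided 0.05) or 0.3% to 0.9% (sign test, one-sided 0.025). Counting TE1 as day 1, RNA is scheduled at TE2, TE4 and TE6, about days 8, 22 and 36, with discretionary repeat draws. Failure before day 30 is therefore possible. For the two-sided sign test with n = 23:

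- 17 of 23 past day 30: p = 0.035.
- 16 of 23 past day 30: p = 0.093.

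On this clock the outcome is open.

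**Selection.** The historical subjects were chosen on prior suppression and CD4 count while on therapy, not on having lasted any time off it. The extension subjects were chosen for 12 failure-free weeks on monotherapy. Even with TE1 as time zero, the two groups do not start from comparable positions.

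**Censoring.** Treatment is open-ended (Synopsis, Total Study Duration), and a subject may return to ART without failing (Section 5.2.1). Some times will be right-censored, and an ordinary rank sum test does not handle that.

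**The case against.** **The SAP may set TE1 as time zero.** This is the strongest reply. Sections 4 and 4.2 treat the first extension dose as the first treatment, and the Synopsis ITT definition requires a dose in the extension study. A reader might infer from the entry criterion that the result is predetermined outright. The documents do not support that: it holds only on the literal wording of the endpoint. But no statement of the endpoint names TE1, and the Synopsis speaks of patients continuing monotherapy.

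**The SAP may hold individual historical times.** Figure 1-1 is a Kaplan-Meier display of the historical cohort. A true second sample would make a rank test possible and remove the 0.083 and 0.069 floors. Individual viral loads might also allow the trial's event to be derived, and a censored-data Wilcoxon test would deal with censoring. This is fair, but it needs a departure from text that reads as a single number.

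**Censoring is a smaller problem than it looks.** A comparison with a fixed 30-day value only needs to know whether each subject passed day 30, so censoring after that day does no harm. A median that is not reached can still be shown to exceed 30 days.

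**Further readings the documents do not support:**

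- That 4 weeks is a third conflicting figure. It agrees with 29 days.
- That the event mismatch favours the drug. Its net direction is unknown.
- That success against 30 days would hide near-total failure by week 48. If the CD 01 average hazard continued, with all 20 non-completers counted as failures, week-48 failure-free survival would be (23/43)^4 = 8%, because 336 days is 4 × 84. That applies the hazard of an unselected cohort to subjects selected for not failing. At a quarter of that hazard the figure is (23/43)^1 = 53%. The documents do not fix a value in this range.

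**The study is proof of concept.** Section 8.6.5 uses this to waive multiplicity adjustment. It does not excuse a primary test that does not fit the design.

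**Conclusion.** The point holds and should be corrected before analysis. The named test does not fit a one-arm study with a constant comparator. The constant is given two values, and it belongs to a different event. Taken literally, the test cannot reach two-sided 0.05 at 23 or 28 subjects. One-sided it could fall below 0.05 (0.042 or 0.034), and since the protocol states neither alpha nor sidedness, it would be too strong to say that significance is impossible.

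On the literal clock a one-sample test against 30 days is decided at enrolment. With TE1 as time zero it is not, but 30 days remains a weak benchmark for long-term maintenance in subjects already selected for 12 failure-free weeks. The literal-clock conclusion needs only a failure-free period longer than 30 days before entry, which criterion 1 provides.

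**What to change.** - State TE1 as time zero wherever the primary endpoint is defined: the Synopsis (Endpoints and Efficacy Analysis) and Sections 2, 8.2.1 and 8.7.4.1.
- In the Synopsis and Section 8.7.4.1, replace the rank sum test with a Kaplan-Meier estimate of time to virologic failure from TE1. Censor subjects without failure at their last viral load on monotherapy. Report the failure-free curve with 95% confidence intervals, and the median with its interval if reached.
- Give one reconciled historical figure together with its event definition, as descriptive context. Dropping every comparison with history is not required. If a formal one is kept, make it a one-sample comparison of the Kaplan-Meier estimate or its interval with that single value on the TE1 clock, and label it a weak benchmark.
- Label any landmark weeks as added late in an open-label study, and state the amendment date and the data known by then. Failures are already reported to the DMC as they occur, so the choice could otherwise be informed by the data.
- Add one sensitivity analysis that counts unplanned ART restart or unplanned discontinuation as failure. The planned restart one week before the end of treatment, and the planned end itself, are not failures.

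**Cost.** A protocol amendment with IRB approval (Section 11.3) and matching SAP text; no new data or visits. The p-value against history becomes weaker or is lost. Intervals are wide: as an illustration without censoring, 16/23 failure-free is 70%, with an exact (Clopper-Pearson) 95% interval of 47% to 87%. The change also comes late, and the report should say so.
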